3.1 Major Secondary Objectives

In addition to our efforts to determine if clazakizumab treatment can significantly reduce or eliminate the severity of cABMR episodes and modify pathologic features (Banff 2015) at the end of 6 months of clazakizumab therapy, we will assess allograft function up to 6-12 M post-transplant, determine renal function using SCr, MDRD GFR (Schwartz equation will be used to estimate CrCl for patients under 18 years of age) calculations and DSA levels. A protocol biopsy will be performed at 6M post-clazakizumab therapy and 12M (for patients who receive 12 doses of clazakizumab). We will also record any late cABMR episodes after clazakizumab therapy. In addition, several immunologic determinations will be assessed at time points before and after initiation of clazakizumab therapy. These include the following:

- Assessment of T_{reg} cells (CD4+,CD25+,FoxP3+CD127^{dim})
- Assessment of T_{fh} cells (CD4+,ICOS+,CXCR5+, IL-21+)
- Assessment of circulating plasmablast (CD19+, CD38+,CD27+, IL-6+)
- > Assessment of CRP, IL-6 levels and Quantitative immunoglobulins by ELISA pre- and post-treatment for cABMR
- Viral PCR monitoring by center protocol for EBV, CMV and Polyoma BK

This study protocol is shown in Figure 14. These secondary end points will help us understand the biology of alloimmune responses to allografts and to determine the ability and mechanisms of clazakizumab's beneficial effects. We will also monitor viral PCRs as per standard-of-care. Long term secondary objectives include:

- 1. determine renal function using SCr, eGFR
- 2. DSA levels
- 3. A protocol biopsy will be performed at 12M, 24M post-clazakizumab LTE.
- 4. record any late cABMR episodes after clazakizumab therapy.
- 5. Assessment of CRP and IgG
- Viral PCR monitoring by center protocol for EBV, CMV and Polyoma BK

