3.2 Inclusion Criteria

- ✓ Age 15-75 years at the time of screening.
- ✓ Biopsy proven cABMR with TG on biopsy as defined by Banff 2015 and DSA + at time of biopsy
- ✓ Subject/Parent/Guardian must be able to understand and provide informed consent.
- ✓ Pneumococcal vaccinated
- ✓ Negative tuberculin ppd result or negative Quantiferon TB gold

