3.3 Exclusion Criteria

- ✓ Multi-organ transplant (e.g. kidney and pancreas)
- √ eGFR < 30 mL/min/1.73m²
- ✓ Advanced Transplant Glomerulopathy (CG3) or advanced IFTA (ct or ci scores ≥3)
- ✓ Previous allergic reactions to monoclonal antibodies.
- ✓ Lactating or pregnant females.

- ✓ Women of child-bearing age and male partners of women of child-bearing age who are not willing or able to practice FDA-approved forms of contraception during study and for 5 months after last dose.
- ✓ HIV-positive subjects.
- ✓ Subjects who test positive for HBV by HBVeAg/DNA or HCV infection [positive Anti-HCV (EIA) and confirmatory HCV RIBA].
- ✓ Subjects with latent or active TB. Subjects must have negative Quantiferon TB gold test result.
- ✓ Recent recipients of any licensed or investigational live attenuated vaccine(s) within two months of the screening visit (including but not limited to any of the following:
 - o Adenovirus [Adenovirus vaccine live oral type 7]
 - Varicella [Varivax]
 - Hepatitis A [VAQTA]
 - Rotavirus [Rotashield]
 - Yellow fever [Y-F-Vax]
 - Measles and mumps [Measles and mumps virus vaccine live]
 - Measles, mumps, and rubella vaccine [M-M-R-II]
 - Sabin oral polio vaccine
 - Rabies vaccines [IMOVAX Rabies I.D., RabAvert])
- ✓ A significantly abnormal general serum screening lab result defined as a WBC < 3.0 X 10³/ml, a Hgb < 8.0 g/dL, a platelet count < 100 X 10³/ml, an SGOT or SGPT > 3X upper limit normal
- ✓ Individuals deemed unable to comply with the protocol.
- ✓ Subjects with active CMV or EBV infection as defined by CMV-specific serology (IgG or IgM) and confirmed by quantitative PCR with or without a compatible illness (Quantitative PCR cut off defined as having > 50 copies of CMV or EBV DNA/PCR)
- ✓ Use of investigational agents within 4 weeks of participation.
- √ History or active Inflammatory Bowel Disease or Diverticular Disease or gastrointestinal perforation
- ✓ Recent infection (within past 6 weeks of screening) requiring any antibiotic use (oral, parenteral or topical).
- ✓ Present or previous (within 5 years) malignancy except for basal cell carcinoma, fully excised squamous cell carcinoma of the skin or non-recurrent (within 5 years) cervical carcinoma-in-situ.

4. Study Design & Methods

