Background: This is a single center, Phase I/II, open label single-arm exploratory study. The trial will primarily examine the safety and tolerability of clazakizumab given after the diagnosis of cABMR in 10 subjects (15-75yrs) who exhibit DSAs to their donor. Patients entered will also have been diagnosed with cABMR + TG post-transplant based on Banff 2015 criteria. Patients are required to have a eGFR \geq 30 mL/min/1.73m² as calculated by the MDRD equation (Schwartz equation will be used to estimate CrCl for patients under 18 years of age) at entry. All patients will be recruited from the renal transplant program at Cedars-Sinai Medical Center. Once cABMR is diagnosed, donor-specific anti-HLA antibodies will be assessed (DSA) which are associated with cABMR and/or graft loss. DSA will be detected using solid phase assay systems currently utilized at the Cedars-Sinai Medical Center HLA Laboratory ([name] Director, [contact]. These anti-HLA antibodies may result naturally or from previous pregnancy, transfusions, or prior transplants. Patients treated with clazakizumab for cABMR will have labs for DSAs, and other monitoring labs as well as immunologic studies as outlined (See Study Protocol in Appendix A). In addition to the standard post-transplant immunosuppressive protocol, patients with cABMR will receive clazakizumab 25mg SC given every 4 weeks (30 days) for a total of 6 doses. If no safety/tolerability/efficacy issues are observed after the initial dose, patients will continue the protocol as outlined (see Appendix A). A protocol biopsy will be performed after the 6th and after the 12th doses of clazakizumab (as mentioned before) to assess the allograft for evidence of cABMR/ABMR, including C4d staining and TG using Banff 2015 criteria¹⁴. Banff scoring will be compared between the index and protocol biopsy after cessation of therapy. Patients who have evidence of persistent allograft dysfunction may have non-protocol biopsies for cause. After completion of the clazakizumab therapy, patients will be followed up to assess allograft function and ABMR episodes as well as DSAs. The protocol is summarized in figure 14 below. Monitoring of Treg, Thir, Tfh and plasmablast as well as IL-6

and CRP level will be performed in the Transplant Immunology Lab at Cedars-Sinai Medical Center at select time points ([name] Director, [contact]).

[figure not shown]

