As indicated previously, the study will be halted and re-evaluated by the Data and Safety Monitoring Board (DSMB) if any patient in the study group develops SAEs or evidence of severe infusion related or infectious complications. In addition the study will be reevaluated if a patient develops worsening ABMR while in treatment, possibly indicating lack of efficacy of clazakizumab (see appendix C).

7 Statistical Analysis

Due to the exploratory nature of this study that involves safety endpoints only and the small sample size that is not powered for efficacy end points, our primary objective will be to assess safety end points and limited efficacy. Most important will be tolerability in the ESRD population and determination of the effects of clazakizumab treatment on circulating DSAs as well as the ability to improve outcomes of patients with cABMR and TG. We will however plan to assess biopsies 6M post-transplantation in patients desensitized with clazakizumab treatment to determine if there are durable effects in prevention of ABMR both acute and chronic.

8 References

- 1. Colvin RB. Antibody-mediated renal allograft rejection: diagnosis and pathogenesis. J Am Soc Nephrol 2007;18:1046-56.
- 8. Sellarés J, de Freitas DG, Mengel M, et al. Understanding the causes of kidney transplant failure: the dominant role of antibody-mediated rejection and nonadherence. Am J Transplant 2012;12:388-99.

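### Section 7 times its biopsy analysis from transplantation, in desensitized patients and for prevention, but the trial treats established cABMR + TG and counts from the first dose

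*Protocol*

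**What the plan says.** Section 7 (Statistical Analysis) closes with a plan to "assess biopsies 6M post-transplantation in patients desensitized with clazakizumab treatment to determine if there are durable effects in prevention of ABMR". Shortly before, it says "Most important will be tolerability in the ESRD population".

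Section 3.1 uses two clocks in one sentence. The aim is to "modify pathologic features (Banff 2015) at the end of 6 months of clazakizumab therapy, we will assess allograft function up to 6-12 M post-transplant", so histology is counted from the start of treatment and function from the transplant.

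The rest of the protocol describes a different setting:

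- **Disease at entry.** Section 3.2 requires "Biopsy proven cABMR with TG on biopsy as defined by Banff 2015 and DSA + at time of biopsy".
- **Renal function at entry.** Section 3.3 excludes "eGFR < 30 mL/min/1.73m".
- **Order of events.** Section 4 has "clazakizumab given after the diagnosis of cABMR in 10 subjects".
- **Biopsies.** Section 4 states: "A protocol biopsy will be performed after the 6th and after the 12th doses of clazakizumab". It compares Banff scores between the index biopsy and the protocol biopsy.
- **Clock.** Appendix A labels the first dose Day 0 and puts the biopsies at Day 180 ± 30 and Day 365 ± 30.
- **Time since transplant.** Sections 3.2 and 3.3 set no limit. Section 4.6 provides for patients who join more than a year after transplant.

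**The concern.** The Section 7 sentence differs from the design in three respects: the clock (transplant rather than first dose), the population (desensitized patients and an ESRD population rather than recipients with a functioning graft and established cABMR + TG) and the aim (prevention rather than change from the index biopsy).

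The clock matters most. This is a single-arm study of 10 subjects, so its biopsy evidence of an effect is the within-patient change from the index biopsy. That comparison needs a time zero at the start of treatment. A time point fixed from transplant can fall before the patient has received any drug, and a biopsy from that time says nothing about clazakizumab. The same holds for graft function under the Section 3.1 limit. A later analysis plan or report that takes its definitions from Section 7 would inherit the error.

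**Working it through.** There is no stated figure to reproduce. The check is a comparison of timelines, followed by a comparison of wording.

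**Inputs**

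- Section 7 time point: 6 months after transplant, taken as 180 days.
- Section 3.1 outer limit for function: 12 months after transplant, taken as 360 days.
- Appendix A: Day 0 is the first dose. The first protocol biopsy is at Day 180 ± 30, that is, Day 150 to Day 210.
- T: days from transplant to first dose. The protocol gives neither a value nor a distribution, so the values of T below are assumptions.

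**Formulas, in study days**

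- Section 7 time point = 180 − T.
- Distance from the planned Day 180 biopsy = 180 − (180 − T) = T.
- Section 3.1 outer limit = 360 − T.

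| Assumed T (days) | Section 7 time point | Section 3.1 outer limit |
|---|---|---|
| 30 | 180 − 30 = Day 150 | 360 − 30 = Day 330 |
| 90 | 180 − 90 = Day 90 | 360 − 90 = Day 270 |
| 180 | 180 − 180 = Day 0 | 360 − 180 = Day 180 |
| 360 | 180 − 360 = Day −180 | 360 − 360 = Day 0 |

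**Thresholds**

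- The Section 7 time point falls inside the Day 150 to 210 window only if 180 − T ≥ 150, so T ≤ 30 days.
- It falls before the first dose if 180 − T < 0, so T > 180 days (about 6 months).
- The Section 3.1 outer limit falls before the first dose if 360 − T < 0, so T > 360 days (about 12 months).
- For the patients foreseen in Section 4.6 (more than a year after transplant), the Section 7 time point lies more than about 180 days before the first dose, and the Section 3.1 limit has already passed.

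**Wording, side by side**

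| Element | Section 7 | Rest of the protocol |
|---|---|---|
| Time zero | transplant | first dose (Appendix A) |
| Population | desensitized; ESRD | cABMR + TG, low eGFR excluded (Sections 3.2, 3.3) |
| Question | prevention of ABMR | change from index biopsy (Section 4) |

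No biopsy in Section 4 or Appendix A is timed from transplant.

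**The later biopsy.** Section 3.1 places the second biopsy at "12M (for patients who receive 12 doses of clazakizumab". Under Section 4, treatment goes on beyond six doses depending on the 6-month findings. The Day 365 biopsies therefore come from a group selected on the earlier result, and a corrected sentence should not treat them as covering all patients.

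**The case against.** The strongest defence is that the right rule already stands elsewhere. Section 4 gives the index-versus-protocol comparison and evaluates function, DSA and Banff scores at 6 months of treatment. Appendix A fixes Day 0. Even within Section 7, the sentence before the faulty one names cABMR and TG. Following the faulty sentence literally would need a biopsy that nobody schedules. The study is small, exploratory and not powered for efficacy. All of this stands. It limits the consequence, but it does not make the sentence correct.

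Several stronger readings are tempting and are not supported:

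- A reader might infer that the biopsy evidence will be lost or that the protocol contains no valid biopsy comparison. Section 4 and Appendix A show otherwise. What is wrong is one stated rule.
- A reader might infer that prevention has no meaning here. Sections 3.1, 4 and 4.3 follow later or recurrent ABMR episodes, so preventing further episodes is a sensible question. It is not what a comparison with the index biopsy measures.
- A reader might take the Section 3.1 phrase as a window opening at 6 months after transplant. The wording gives an upper limit only, and the argument above uses only that limit.
- A reader might infer that the wording was carried over from the earlier tocilizumab desensitization trial in Section 1.3, which took biopsies 6 months after transplant. The protocol does not say so, and nothing here depends on it.

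The timing language elsewhere is also not perfectly uniform. Section 3.1 speaks of 6 months post-therapy and Section 4 of cessation of therapy, while Appendix A lists a seventh dose in the Day 180 column. None of these counts from transplant.

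**Conclusion.** The point holds as an internal contradiction that should be corrected. As written, the Section 7 biopsy rule matches the planned Day 180 biopsy only for patients first dosed within about 30 days of transplant, and it points to a time before any drug for those first dosed more than 6 months after it. The Section 3.1 limit has the same fault beyond 12 months.

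How many patients this touches cannot be stated, because the protocol gives no distribution of time since transplant. Section 4.6 shows only that enrolment beyond one year is foreseen. The thresholds assume 30-day months. Confidence in the contradiction is high. Its consequence is a misdirected analysis definition, with no loss of data and no effect on sample size.

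**What to change.** Replace the last sentence of Section 7 with:

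> Time zero is the first dose. Banff 2015 scores on the Day 180 protocol biopsy will be compared with the index biopsy in patients with cABMR + TG, on the intent-to-treat basis of Section 4; the Day 365 biopsy comparison is descriptive, because it covers patients who continued treatment on the basis of their 6-month result. ABMR episodes after the first dose will be described.

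In the preceding text of Section 7, replace the reference to an ESRD population with kidney transplant recipients with cABMR + TG. In Section 3.1, count allograft function from the first dose instead of from transplant.

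The cost is a text amendment to two sections. No visit, biopsy, sample, dose or clinical rule changes. If a statistical analysis plan exists, its biopsy and function definitions should be checked against the corrected wording.

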Appendix C: DSMB Charter & FDA Guidance for Clinical Trial Sponsors

Appendix D: Safety Reporting Forms

Appendix E Study/Protocol: A Phase I/II Trial to Evaluate the Safety and Tolerability of Clazakizumab® (Anti-IL-6 monoclonal) As an Agent to Eliminate Donor Specific HLA Antibodies (DSAs) and Improve Outcomes of Patients with Chronic & Active Antibody-Mediated Rejection (cABMR) Post-Kidney Transplantation

The below schedule to repeat annually (Visit 1 – 6) per PI discretion

Study visit	Visit 1 Follow up	Visit 2 Week 8 -	Visit 3 Week 16	Visit 4 Week 24 -	Visit 5 Week 32-	Visit 6 Week 40-
		7d/+	-7d/+	7d/+	7d/+	7d/+
	year Day 0	10days	1 '	10days		
	CLAZ#1 %	Todays	10days	Todays	10days	10days
NA - P - 11P - 1	CLAZ#1 %	-	+		-	
Medical History			-			
Complete Physical Exam						
Vital signs/weight	X	X	X	X	X	X
Safety laboratory tests	х	Х	x	х	х	X
(CBC with differential, CMP, UA) [^]	^	^				
EBV, CMV, PBK DNA PCR^				X		
IgG^				Х		
CRP^				Х		
Donor – specific antibodies (DSA)^						
CNI Levels^	X	X	X	X	X	X
TB testing [Quantiferon TB Gold]						
Clazakizumab injection	X #1%	X #2	X #3	X #4	X #5	X #6
Estimated GFR (using MDRD equation or Schwartz						
equation will be used to estimate CrCl for patients	X	X	X	X	X	X
under 18 years of age)						
Pregnancy test (for WOCP) ²	X	X	X	X	X	X
Concomitant Med Review	Х	Х	X	Х	Х	Х
Kidney Biopsy						
Review of allograft loss						
Review of non-protocol biopsy results						
Adverse Event Monitoring	X	Х	X	Х	Х	Х

Day 365 ± 30 days #
X#
X#
X#
X#
X#
X#
X&#	

	

	

	

	

	

V##	

X*#	

X# X#	

A#	

	

& TB testing to be

completed once a year. TB test will be collected if not done in the last 2 months.

- ^ At or within 1 month prior to appointment
- 1. DSA to be collected prior to clazakizumab infusion.
- 2. Women of child bearing age is between 12-55 years old.
- * At 12 Months Per PI discretion (any other biopsies will be conducted for cause)
- % Timed minimum 4 weeks from last clazakizumab dose
- # Visit should be combined with either visit 1, 2, 3, 5, or 6. Depending on which visit is closest to day 365

Study visit	Visit 1	Visit 2	Visit 3	Visit 4	Visit 5	Visit 6
	Follow up	Week 4	Week 8	Week 12	Week 16	Week 20
	year	-2d/+	-2d/+	-2d/+	-2d/+	-2d/+
	CLAZ#1 %	10days	10days	10days	10days	10days
Medical History						
Complete Physical Exam						
Vital signs/weight	X	X	X	X	X	X
Safety laboratory tests	х	Х	X	X	X	Х
(CBC with differential, CMP, UA) [^]	^	^	^	^	^	^
EBV, CMV, PBK DNA PCR^						X
IgG^						X
CRP^						X
Donor –specific antibodies (DSA)^						
CNI Levels^	X	X	X	X	X	X
TB testing [Quantiferon TB Gold]						
Clazakizumab injection	X #1 %	X #2	X #3	X #4	X #5	X #6
Estimated GFR (using MDRD equation or						
Schwartz equation will be used to estimate	Х	X	X	X	X	X
CrCl for patients under 18 years of age)	ļ		 	 		
Pregnancy test (for WOCP) ²	X	X	X	X	X	X
Concomitant Med Review	X	X	X	X	X	X
Kidney Biopsy						
Review of allograft loss						
Review of non-protocol biopsy results						
Adverse Event Monitoring	X	X	X	X	X	X

Day 365
± 30
days#
uays#
X#
X#
X#
X# X#
X#
X#
Λ#
X &#	

	

	

	

	

	

	

	

X *#	

X#	

X#	

	

	

[&]amp; TB testing to be completed once a year. TB test will be collected if not done in the last 2 months.

[^] At or within 1 month prior to appointment

^{1.} DSA to be collected prior to clazakizumab infusion.

^{2.} Women of child bearing age is between 12-55 years old.

^{*} At 12 Months Per PI discretion (any other biopsies will be conducted for cause)

[%] Timed minimum 4 weeks from last clazakizumab dose

[#] Visit should be combined with either visit 1, 2, 3, 4 or 5. Depending on which visit is closest to day 365
